#### Inclusion criteria:

- Diagnosis of invasive non-metastatic breast cancer (i.e. stage I to III);
- Breast cancer diagnosis  $\geq 18$  and  $\leq 40$  years;
- No prior history of gonadotoxic treatments;
- Fertility preservation counseling for fertility preservation;
- Written inform consent;
- FSH  $< 20$  UI/L and/or antra-follicular count  $\geq 6$  (follicles of 2-9 mm) and/or AMH  $\geq 6$  pmol (only applicable for patients who undergo controlled ovarian stimulation for embryo/oocyte cryopreservation).

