**Table 1. Schedule of assessment for correlative research**

	Inclusion (diagnosis)	M 0-1 (start of COS)	M 0-1 (end of COS)	M4-6 (end of CT)	M 16-18 (12 M after CT)	M 28-30 (24 M after CT)	M 60 (5 y after diagnosis)	Relapse
Serum (AMH, FSH, E2)	x			x	x	x	x	
Serum (Progesterone/E2)		x*	x**					
Plasma for ctDNA	x		x					x
Whole blood	x							
1 block of FFPE of primary tumor s	x							

x: mandatory

\$: 15 representative slides of 10 µm should be provided.

\*: Can be performed at the inclusion if COS start within 5days

\*\* : serum samples at L3 and L8 will be collected

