## 4.3. Laboratory procedures for ovarian reserve and function biomarker analysis

This constitutes serum evaluation of anti-mullerian hormone (AMH), follicle stimulating hormone (FSH), estradiol (E2) and serum progesterone. Hormonal measurement for the study will be centrally performed at the LHUB (Laboratoire Hospitalier Universitaire de Bruxelles). Elecsys® AMH module (Roche Diagnostics, Vilvoorde, Belgium) is used for AMH measurement. Estradiol and progesterone are assayed by electrochemiluminescence immuno-assay using a competitive immunoassay (Modular E170—Roche diagnostics, Germany). The inter-assay coefficient of variation was less than 5% for all assays.

The evaluation of AMH, FSH, and E2 will be done at enrollment (i.e. at the time of oncofertility counseling/breast cancer diagnosis) before starting chemotherapy (and before starting controlled ovarian stimulation in patients who access oocyte/embryo cryopreservation). Then, these analyses will be repeated at the end of chemotherapy, 12 and 24 months after the end of chemotherapy, and finally 5 years after diagnosis. At all time points, a 5ml of blood sample should be collected. After blood clotting, each tube should be centrifuged at 2600g for 10 minutes and serum should be collected

in 1mL aliquots. For each sample, two 1mL aliquots are required. Aliquots should be stored at  $-80^{\circ}\text{C}$ . The aim of these analyses is to evaluate the impact of anticancer treatment on ovarian reserve (i.e. AMH) and ovarian function parameters (FSH, E2).

Serum progesterone and E2 will be evaluated the first day and at the end of controlled ovarian stimulation (trigger day). A 5ml of blood sample should be collected. After blood clotting, each tube should be centrifuged at 2600g for 10 minutes and serum should be collected in 1mL aliquots. For each sample, one 1mL aliquot is required. Aliquots should be stored at  $-80^{\circ}\text{C}$ .

All samples will be shipped to the central laboratory (Erasmus hospital) at fixed time points for analysis.

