- Type of stimulation: follicular or random;
- Total follicle-stimulating hormone (FSH) dose;
- Number of stimulation days;
- Number of days with antagonist;
- Progesterone and Estradiol levels at trigger;
- Progesterone level at triggering and during luteal phase (if available).

In patients who return to the fertility clinic after the end of treatment, to evaluate the type and outcomes of assisted reproductive technology procedures used, the following endpoints will be evaluated:

- Number of patients who returned to fertility clinic;
- Type of assisted reproductive technology procedures used;
- Number of embryos transferred;
- Pregnancy rate: defined by  $\beta$ -hCG determination 14 days after embryo transfer;
- Clinical pregnancy rate: defined as the presence of at least one gestational sac at the time of the first ultrasound examination by the eight week of gestation;
- Implantation rate per embryo transfer: defined as the ratio between the number of visible sacs 4 weeks after embryo transfer and the number of embryos transferred.

In patients with a clinically confirmed pregnancy obtained with assisted reproductive technology procedures after the end of treatment, pregnancy, fetal and obstetrical outcomes of the pregnancies will be evaluated. The following endpoints will be evaluated:

- Miscarriage rate;
- Live birth rate per embryo transfer: defined as the number of births of live infants beyond viability (> 24 weeks);
- Twinning rate;
- Premature delivery: <37 weeks of gestation;
- Malformation rate with number and types of malformations;
- Obstetrical complication rate with number and types of complications.

Finally, to evaluate the impact of anticancer therapies (chemotherapy with or without endocrine therapy with or without anti-HER2 agents) on patients' ovarian function, the following endpoints will be evaluated:

- Incidence of treatment-induced amenorrhea one year after the end of chemotherapy;
- Incidence of treatment-induced amenorrhea two years after the end of chemotherapy;

- Incidence of treatment-induced amenorrhea five years after the end of chemotherapy;
- Age at menopause defined as no menstrual period for more than 12 months irrespectively of menstrual resumption after chemotherapy;
- AMH values one year after the end of chemotherapy;
- AMH values two years after the end of chemotherapy;
- AMH values five years after the end of chemotherapy.

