The impact of anticancer therapies on patients' ovarian function will be evaluated in various subgroups of young breast cancer patients according to:

- Age: <30 vs. 30-35 vs. > 35;
- Type of chemotherapy received: anthracycline- and taxane-based vs. taxane-based vs. others;
- Number of months of chemotherapy received: <4 months vs. > 4 months;
- Exposure to platinum agents: use vs. no use.
- Exposure to endocrine therapy: use vs. no use.
- Exposure to anti-HER2 therapy: use vs. no use.
- Presence of *BRCA* mutation: *BRCA*-mutated vs. *BRCA*-not mutated.

The sample size has been estimated based on the study primary endpoint (i.e. number of mature oocytes collected). With 113 patients in the standard-stimulated cohort and 113 in the letrozole-stimulated cohort, assuming a mean number of mature oocytes collected of 6.1 in the standard-stimulated cohort, the study will have a power of 0.80 to reject the null hypothesis of equal means when the population mean difference is 1.5 mature oocytes collected (estimating a mean number of mature oocytes collected of 7.6 in the letrozole-stimulated cohort) with a standard deviation for both groups of 4.0 and with a significance level (alpha) of 0.05 using a two-sided two-sample equal-variance t-test. Considering that approximately one out of three (1:3) eligible patients counseled to

undergo controlled ovarian stimulation for oocyte cryopreservation before starting anticancer treatments will accept the procedure, it is estimated to enroll 339 patients in the non-stimulated cohort.

Patients demographic, clinical and pathologic baseline characteristics will be compared in the three cohorts using chi-square test or Fisher Exact test for categorical variables and Wilcoxon rank-sum test or t-test for continuous variables, as appropriate.

Dicothomous outcomes will be compared using univariate and multivariate logistic regression models. Time-to-event outcomes will be estimated and plotted using Kaplan-Meier methods. Survival rates will be compared using log-rank test and Cox proportional hazards models for univariate and multivariate analysis, respectively.

All tests will be two-sided and p-values of  $< 0.05$  will be considered statistically significant.

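### Over about five years of observation, age at menopause in women diagnosed at 40 or younger largely restates age at diagnosis; compare time to menopause across subgroups instead

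*Combined protocol and SAP*

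**What the plan says.** Section 5 gives seven endpoints for the effect of anticancer therapy on ovarian function: treatment-induced amenorrhoea at one, two and five years after chemotherapy, AMH at the same three times, and "Age at menopause defined as no menstrual period for more than 12 months irrespectively of menstrual resumption after chemotherapy". It then has the effect on ovarian function evaluated in subgroups. The first is "Age: <30 vs. 30-35 vs. > 35"; the others are chemotherapy type and duration, platinum, endocrine therapy, anti-HER2 therapy and BRCA status.

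Section 3.1 admits women diagnosed at ages 18 to 40. Table 1 is titled "Schedule of assessment for correlative research" and ends, relapse sampling apart, at month 60 after diagnosis. Section 4.3 places the post-chemotherapy hormone samples at "12 and 24 months after the end of chemotherapy, and finally 5 years after diagnosis". Section 5 goes slightly further with "Incidence of treatment-induced amenorrhea five years after the end of chemotherapy". No section states the total length of follow-up.

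Section 5 defines iDFS, BCFI and OS as times from study inclusion. It gives age at menopause no time origin, censoring rule or named method.

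**The concern.** A woman diagnosed at 40 or younger and followed for about five years has an observed age at menopause only if her periods stop early enough in that window for more than 12 months without menses to be confirmed. Everyone else has no value. A value that does exist is age at diagnosis plus a short delay.

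The average of such values shows mainly how old the women were when diagnosed. It does not show how many lost ovarian function, and barely shows how soon. Set out by age band, it would make the youngest women appear to reach menopause earliest, even if ovarian failure were far commoner in the oldest. Between regimens, a difference in age at diagnosis could pass for a treatment effect.

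**Working it through.** **The plan's own figure.** None is given for this endpoint. The only sample-size calculation (113 per stimulated cohort; difference 1.5 mature oocytes, SD 4.0, two-sided alpha 0.05, power 0.80) reproduces: the t-test needs 112.6 per group, so 113, with power 0.801. It does not enter the check below.

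**Inputs from the documents.** Age at diagnosis 18 to 40 (Section 3.1); bands <30, 30-35 and >35 (Section 5); last hormone sample at month 60 and end of chemotherapy at months 4 to 6 (Table 1); amenorrhoea and AMH five years after chemotherapy (Section 5); more than 12 months without menses (Section 5).

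**Step 1, horizon.** Five years after chemotherapy is 60 + 4 to 60 + 6 = month 64 to 66. The last named time points therefore give H = 60/12 = 5.0 to 66/12 = 5.5 years after diagnosis.

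**Step 2, possible values.** The last period must fall at least 12 months before H, so the delay from diagnosis lies between 0 and H − 1 = 4.0 to 4.5 years. The plan does not say whether menopause is dated at the last period or at confirmation one year later. Reading the bands in completed years (<30; 30 to <36; 36 to <41), the ranges for H = 5.0, with the upper limit for H = 5.5 in brackets, are:

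| Band | Dated at last period | Dated at confirmation |
|---|---|---|
| <30 | 18 to 34 (34.5) | 19 to 35 (35.5) |
| 30-35 | 30 to 40 (40.5) | 31 to 41 (41.5) |
| >35 | 36 to 45 (45.5) | 37 to 46 (46.5) |

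The outer bands do not meet under either dating rule. With exact decimal ages, >35 starts just above 35 (or 36 at confirmation), still above 34.5 (or 35.5). They could meet only if 30 + (H − 1) exceeded 35, that is, with H above 6 years. Adjacent bands do overlap: dated at last period, over 30 to 34 (34.5) and 36 to 40 (40.5).

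**Step 3, largest shift treatment could cause.** Assume ages among women with an event are uniform within each band, with means 24, 33 and 38.5. Even if every event in the younger band came as late as possible and every event in the older band at once, the gap in means is the gap between midpoints minus H − 1:

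- 30-35 minus <30: 9 − 4 = 5.0 years (9 − 4.5 = 4.5).
- >35 minus 30-35: 5.5 − 4 = 1.5 years (5.5 − 4.5 = 1.0).
- >35 minus <30: 14.5 − 4 = 10.5 years (14.5 − 4.5 = 10.0).

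The order cannot reverse.

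**Step 4, opposite treatment effects.** Assume a constant yearly hazard h and H = 5.0. The share with an observed value is 1 − exp(−4h). The mean delay among them is 1/h − 4·exp(−4h)/(1 − exp(−4h)), which is 1.97, 1.93 and 1.74 years for h = 0.02, 0.05 and 0.20.

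| Hazards (<30, 30-35, >35) | Share with a value | Mean observed age |
|---|---|---|
| 0.02, 0.05, 0.20 | 7.7%, 18.1%, 55.1% | 26.0, 34.9, 40.2 |
| 0.20, 0.05, 0.02 | 55.1%, 18.1%, 7.7% | 25.7, 34.9, 40.5 |

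Incidence is fully reversed and the endpoint hardly moves. Simulation under five sets of hazards (0.02 to 0.6 per year) gave means of 25.5-26.0, 34.9 and 39.8-40.5. A woman from 30-35 had a later observed age than one from >35 in 2.1-3.5% of random pairs. For <30 against 30-35 it was 0.6-1.0%, and for <30 against >35 it was zero.

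**Step 5, the other subgroups.** With a delay uniform over w years and independent of age, age at diagnosis accounts for Var(age)/(Var(age) + w²/12) of the variance of observed age. For ages uniform over 18-41 (SD 6.63): 44.1/(44.1 + 1.33) = 97% at w = 4 and 44.1/(44.1 + 1.69) = 96% at w = 4.5. For ages peaking at 38 (SD 5.11): 26.1/(26.1 + 1.33) = 95% and 26.1/(26.1 + 1.69) = 94%. From Step 4, a tenfold rise in hazard lowers the mean by only 1.97 − 1.74 = 0.23 year, so a one-year imbalance in age at diagnosis between two regimens would outweigh it.

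**The case against.** **The five-year limit is an inference.** Table 1 and Section 4.3 schedule samples, not menstrual follow-up. The case report form carries age at menopause with no time limit, and Section 5 itself expects menstrual data past month 60. This stands. A reader might infer that the plan ends menstrual follow-up at five years; the documents do not say so. They name no later ovarian time point either.

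**The plan does not say that mean observed ages will be compared, and it provides Kaplan-Meier methods for time-to-event outcomes.** The first half is fair. The Kaplan-Meier sentence does not settle the matter, because age at menopause has no time origin or censoring rule. A curve on the age scale would also mislead without delayed entry, since a woman enrolled at 38 cannot have an observed menopause before 38.

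**Values are not fixed by age at diagnosis, and the bands are not all separate.** Correct. A reader might infer complete separation, but values are bounded within a window and adjacent bands overlap. Only the outer bands are separate on this horizon.

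**The other subgroup results are not predetermined.** Also correct: the problem there is confounding by age and the omission of women without an event.

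**The objective has other endpoints.** Amenorrhoea incidence and AMH at one, two and five years would be expected to show a real difference in ovarian damage. This stands and limits the importance of the point.

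**Conclusion.** The point holds for one secondary endpoint, and the plan should be changed. On a horizon of about 5 to 5.5 years, the order of mean observed age at menopause across the age bands follows from the band limits and carries almost no information on treatment. In the other subgroups age at diagnosis would account for roughly 94-97% of the variance unless adjusted for.

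The ranges in Step 2 rest on the documents' figures, the inferred horizon and the completed-years reading of age. Non-overlap of the outer bands also survives decimal ages if one dating rule is used throughout. The order of adjacent band means, and the figures in Steps 3 to 5, rest on assumed age distributions and hazards, because the documents give neither. Somewhat longer follow-up would ease the problem without removing it.

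It would be too strong to conclude that the ovarian-function objective cannot be answered: six of its seven endpoints are unaffected by this point.

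**What to change.** In Section 5, replace age at menopause as the compared endpoint with time from diagnosis to menopause, and:

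- state the follow-up horizon, reconciling five years after diagnosis with five years after chemotherapy;
- say whether menopause is dated at the last period or at confirmation;
- censor women still menstruating at last follow-up, and treat death and gynaecological prophylactic surgery as competing events;
- report 5-year cumulative incidence by subgroup, adjusting the non-age comparisons for age at diagnosis;
- keep age at menopause as a descriptive listing, not compared across age bands.

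The cost is mainly wording. Section 3.2 already collects age and date at diagnosis, age at menopause, date of last follow-up or death, and the date of gynaecological prophylactic surgery (listed under the germline-mutation item). Diagnosis is the practical origin, because no chemotherapy start date is listed. One small downside remains: if age at menopause is recorded only in whole years, timing is accurate to about one year within a window of about five. Recording the date of last menses would remove that limit at the price of one extra form item.

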### 3.2. Data collection

For all consecutive eligible patients included in the study, anonymized data will be entered into ad hoc electronic Case Report Forms (eCRF). The following information will be collected:

1) Baseline characteristics (at study inclusion): BMI; smoking habit; age at menarche; use of birth control pills; prior children before breast cancer diagnosis; history of spontaneous or induced abortion; prior treatment for infertility; prior gynecological surgery and/or medical history with possible impact on fertility; baseline AMH value.

- 2) Breast cancer history: date of diagnosis; age at diagnosis; disease stage; type of breast and axillary surgery; histology; tumor size and nodal status (for patients who underwent primary systemic therapy, both clinical tumor size and nodal status before treatment initiation and pathological tumor size and nodal status at the time of surgery will be collected); grade; hormone receptor status (estrogen and progesterone receptors); HER2 status.
- 3) Treatment of the primary tumor: timing of systemic therapy administration (adjuvant or neoadjuvant); use of chemotherapy (type and number of cycles); use of endocrine therapy (type and duration); use of anti-HER2 targeted therapy (type and duration); use of radiotherapy; use of breast reconstruction surgery.
- 4) Survival status: any recurrence of invasive breast cancer including date of the event; type of recurrence of invasive breast cancer (locoregional or distant event); any second primary contralateral breast cancer including date of the event; any second primary malignancy including date of the event; date of last follow-up and/or death.
- 5) Controlled ovarian stimulation protocol: type of stimulation (follicular or random); total FSH dose; number of stimulation days; number of days with antagonist; estradiol and progesterone levels at triggering and during luteal phase (L3-L8); number of oocyte/embryo collected; number of mature oocytes collected; maturation rate; number of oocyte/embryo cryopreserved; number of patients with poor response; number of patients with stimulation failure.
- 6) Ovarian function before and after chemotherapy: treatment-induced amenorrhea; age at menopause; AMH values.
- 7) Pregnancy after breast cancer: any pregnancy including date of the event; pregnancy outcome; gestational age at delivery; pregnancy/fetal/obstetrical outcomes; breastfeeding and its duration; use and type of assisted reproductive technology.

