8) Presence of germline *BRCA* mutation or other type of germline mutations (if available): date of genetic testing; type of mutation; use and date of breast prophylactic surgery; use and date of gynecological prophylactic surgery.

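### The menopause and amenorrhea endpoints have no rule for gynecological surgery or ovarian suppression, which puts the BRCA and endocrine-therapy contrasts at risk of serious bias

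*Combined protocol and SAP*

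**What the plan says.** Section 5 (Statistics) introduces the ovarian-function endpoints with this aim: "to evaluate the impact of anticancer therapies (chemotherapy with or without endocrine therapy with or without anti-HER2 agents) on patients' ovarian function". The list that follows has three kinds of endpoint:

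- Amenorrhea at three times, the first worded "Incidence of treatment-induced amenorrhea one year after the end of chemotherapy", then at two and five years. No duration, assessment window or cause is attached.
- Menopause: "Age at menopause defined as no menstrual period for more than 12 months irrespectively of menstrual resumption after chemotherapy".
- AMH at one, two and five years after chemotherapy.

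The subgroup list for these endpoints includes "Exposure to endocrine therapy: use vs. no use" and "Presence of *BRCA* mutation: *BRCA*-mutated vs. *BRCA*-not mutated". Binary outcomes go to univariate and multivariate logistic regression, with no covariates named.

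Section 3.2 (Data collection) records "use of endocrine therapy (type and duration"), and under ovarian function "treatment-induced amenorrhea; age at menopause; AMH values". Under the germline-mutation item, which is marked as collected if available, it records "use and date of gynecological prophylactic surgery". Section 5 does not use the surgery date. Neither section records the cause of amenorrhea or whether a woman is under suppression at the visit.

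**The concern.** A woman whose ovaries or uterus have been removed meets the menopause rule after 12 months, whatever anticancer treatment did to her ovaries. So does a woman whose periods are held off by a suppressing drug. For amenorrhea, nothing tells the analyst which way to classify either woman.

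This matters most for two of the planned contrasts. Section 3.2 itself places prophylactic gynecological surgery under the germline-mutation item, so surgery is likely to be unevenly spread across the BRCA groups. Suppression, where it is given as endocrine therapy, would occur only among endocrine-therapy users. In each contrast the grouping factor helps decide who is misclassified. A difference could then appear with no difference in lasting ovarian function, and it would feed into the counseling that the study is meant to improve.

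**Working it through.** **The plan's own figures.** There is none for these endpoints. The plan's one power calculation, for the primary endpoint, reproduces: a difference of 1.5 with SD 4.0, two-sided 0.05 and power 0.80 needs 112.6, so 113 per cohort (power 0.801). It has no bearing on this point.

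**Inputs.** From the documents: cohort sizes 113 + 113 + 339 = 565, and two-sided 0.05. Assumed, because the documents give no values: the true rate p of lasting amenorrhea, equal in both subgroups, and the share s of one subgroup without periods only because of surgery or suppression (zero in the other subgroup).

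**Step 1: apparent rate.** Observed rate q = s + (1 − s)p. Odds ratio = [q/(1 − q)] / [p/(1 − p)].

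At p = 20%:
- s = 10%: q = 0.10 + 0.90 × 0.20 = 28%; odds ratio (0.28/0.72)/(0.20/0.80) = 1.56
- s = 20%: q = 0.20 + 0.80 × 0.20 = 36%; odds ratio (0.36/0.64)/0.25 = 2.25
- s = 30%: q = 0.30 + 0.70 × 0.20 = 44%; odds ratio (0.44/0.56)/0.25 = 3.14

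For the same three shares, p = 10% gives odds ratios of 2.11, 3.50 and 5.29, and p = 40% gives 1.28, 1.62 and 2.07. At s = 0 the odds ratio is 1.

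**Step 2: chance of a nominally significant difference.** For subgroup sizes n1 and n2, use Φ[(d − 1.96·se0)/se1], where d = q − p, se0 is the pooled and se1 the unpooled standard error of the difference. All 565 women are taken as evaluable. Further assumptions: 50–70% use endocrine therapy and 10–20% carry a BRCA mutation.

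| p | s | Endocrine contrast | BRCA contrast |
|---|---|---|---|
| 20% | 10% | 0.52–0.61 | 0.31–0.46 |
| 20% | 20% | 0.98–0.99 | 0.76–0.93 |
| 40% | 10% | 0.26–0.30 | 0.14–0.21 |
| 40% | 20% | 0.75–0.82 | 0.41–0.64 |

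The nominal value is 0.05. Losses to follow-up or untested BRCA status would lower these probabilities but leave the Step 1 bias unchanged.

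**Step 3: would excluding suppressed women solve it?** Not safely. Suppose suppression goes only to women still menstruating, with p = 20%. Dropping 30%, 50% or 70% of users leaves 20/70 = 29%, 20/50 = 40% or 20/30 = 67% amenorrheic against 20%. The odds ratios are 1.6, 2.7 and 8.0. Exclusion can replace one bias with another.

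**Step 4: can hormone results arbitrate?** Only in part. Table 1 and Section 4.3 place the last AMH, FSH and E2 sample five years after diagnosis (M60). Table 1 puts the end of chemotherapy at M4–6, so five years after chemotherapy is M64–66, when no sample is scheduled. Samples at fixed visits also cannot date menopause.

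**The case against.** A reader might infer that the endpoints count suppressed or operated women as treatment-induced ovarian failure, so that both subgroup results are wrong by construction. The documents do not support that, for four reasons.

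- Treatment-induced amenorrhea is undefined. The plan is silent; it does not say that such women are counted, and elective prophylactic surgery is arguably outside the term. No endpoint is called ovarian failure.
- The objective expressly includes endocrine therapy. Amenorrhea during such therapy is arguably part of the effect to be measured. What remains is that temporary and lasting effects are not separated.
- The documents never say that endocrine therapy includes ovarian suppression. Outside the stimulation protocols, GnRH analogues appear only as a fertility-preservation procedure allowed in the non-stimulated cohort. The drug half of the concern is an inference. Nor is the recorded gynecological surgery specified as removal of ovaries or uterus.
- The affected shares have no source in the documents, and the bias vanishes when they are zero.

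These points limit how certain the concern is, but they do not remove it. Surgery is not among the therapies named in the objective, so the second point does not cover the BRCA contrast. AMH is a useful non-menstrual companion endpoint, but it does not rescue that contrast, because removing the ovaries also removes AMH. Collecting surgery dates and endocrine-therapy type does not help while no rule uses them, and adjustment in an unspecified logistic model cannot repair an outcome that surgery itself determines.

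**Conclusion.** The concern holds in a limited form. The menopause rule takes no account of cause, amenorrhea is undefined, and neither endpoint has a rule for surgery or suppression. The BRCA and endocrine-therapy contrasts are therefore at risk of serious bias, but not certain to be biased. At an assumed true rate of 20%, an affected share of 10–30% in one group produces odds ratios of 1.6 to 3.1 where the true value is 1. Across assumed true rates of 10% to 40%, the range is 1.3 to 5.3. All of this rests on assumed rates and on the affected share being zero in the comparison group. The surgical part is the firmer one; the suppression part depends on what endocrine therapy turns out to include.

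These are subgroup contrasts within a secondary objective. The primary endpoint, the sample size and the oncological safety analyses are untouched. The change should be made, but the study's main conclusions do not depend on it.

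**What to change.** In Section 5, define treatment-induced amenorrhea (duration, assessment window, cause), and then:

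1. **Age at menopause.** Censor at the recorded date of gynecological prophylactic surgery that removes the ovaries or uterus, or treat that surgery as a competing event.
2. **Amenorrhea and AMH at one, two and five years.** These are fixed-time outcomes, for which censoring in a logistic model has no meaning. Report women with such prior surgery as a separate category, not as treatment-induced events, and base the BRCA contrast on this.
3. **Endocrine-therapy contrast.** Report amenorrhea under ovarian suppression separately from amenorrhea off suppression, using the endocrine-therapy type and duration already collected. Keep the all-cause result alongside; do not exclude these women.
4. **FSH and E2.** Use them only as supporting evidence, off suppression and where a sample is scheduled. Reconcile the five-year endpoint with the M60 sample.

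In the eCRF, add suppression status at the visit and type of gynecological surgery, and record the surgery date for all women, not only under the germline item.

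The cost is protocol wording, derivation code and a few simple fields, best added while data are being collected prospectively. The downside is smaller cells in the subgroup tables.

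### Section 5 specifies no analysis of post-chemotherapy AMH that uses the inclusion AMH sample, so subgroup differences present before treatment can be read as differences in treatment impact

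*Combined protocol and SAP*

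**What the plan says.** The last aim listed in Section 5 is "to evaluate the impact of anticancer therapies (chemotherapy with or without endocrine therapy with or without anti-HER2 agents) on patients' ovarian function". Three of its endpoints concern AMH: "AMH values one year after the end of chemotherapy", "AMH values two years after the end of chemotherapy" and "AMH values five years after the end of chemotherapy". Each is a level at follow-up. No change, ratio, recovery threshold or adjusted comparison is defined.

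Section 5 then evaluates impact in subgroups by age (three bands), type and duration of chemotherapy, platinum, endocrine therapy, anti-HER2 therapy and BRCA status.

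The reference sample exists. Section 3.2 lists "baseline AMH value" among the data taken at inclusion. Table 1 marks serum AMH at inclusion as mandatory. Section 4.3 states "The evaluation of AMH, FSH, and E2 will be done at enrollment", before chemotherapy and before any stimulation, and gives the purpose of the whole series as evaluating what treatment does to ovarian reserve.

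In Section 5, baseline ovarian reserve appears once, as a descriptive characteristic of women who undergo stimulation. The named methods are logistic regression for dichotomous outcomes, and Kaplan-Meier, log-rank and Cox methods for time-to-event outcomes. The t-test and Wilcoxon test are assigned to baseline characteristics. No method is given for a continuous outcome.

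**The concern.** Impact of treatment means what treatment changed. A follow-up level combines what treatment removed with what was there beforehand. If two subgroups entered with different AMH and lost the same fraction, their follow-up levels still differ, and under an impact objective that difference invites a causal reading.

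The risk is most direct for age and BRCA status, which are fixed before treatment. For treatment-exposure subgroups it arises only if baseline reserve, or age, differs by the treatment received.

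Section 1 says the results are meant to improve oncofertility counseling. The practical error would be to tell one group of women that chemotherapy harms their reserve more, when they may simply have started lower.

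**Working it through.** **1. The plan's own figures.** The only sample-size calculation concerns mature oocytes: difference 1.5, SD 4.0, two-sided alpha 0.05, power 0.80, 113 per stimulated cohort. The normal approximation gives n = 2 × (1.960 + 0.842)² × 4.0² / 1.5² ≈ 112 per cohort. With 113, exact t-test power is 0.801. The figure reproduces, but it says nothing about AMH. The documents give no AMH mean, SD, correlation or power, so every AMH input below is an assumption.

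**2. Equal proportional loss.** Let baseline geometric means be A and B, and let treatment leave the same fraction k in both groups. The follow-up ratio is (A × k)/(B × k) = A/B. If women under 30 start 1.5 to 2.5 times higher than women over 35 (assumed), the raw follow-up comparison shows the same 1.5 to 2.5-fold gap, although the difference in proportional impact is nil.

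**3. How often a raw comparison would mislead.** Assume log-AMH at follow-up equals log-AMH at baseline, minus a common loss, plus noise. Let the baseline gap be d baseline SDs and the baseline-to-follow-up correlation be rho. The raw follow-up gap is then d × rho follow-up SDs, and the test's expected z is d × rho / √(1/n1 + 1/n2).

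Take all 113 + 113 + 339 = 565 women, split equally, with no loss to follow-up (also assumed). For d = 0.5 and rho = 0.5, z = 0.25 / √(2/282.5) = 0.25 / 0.0841 = 2.97, and a two-sided 5% test rejects in 84.4% of trials. The other rejection rates, with true impact identical, are:

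| d | rho = 0.3 | rho = 0.5 | rho = 0.7 |
|---|---|---|---|
| 0.25 | 14.5% | 31.8% | 54.8% |
| 0.50 | 43.0% | 84.4% | 98.6% |

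At d = 0.5 and rho = 0.5 the rate is 66.2% with a 20/80 split of 565, and 46.8% with 226 women split equally. In simulations of 3,000 runs per setting, change in log-AMH rejected in 4.5% to 5.6% of runs and the baseline-adjusted model in 4.7% to 5.4%.

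**4. What step 3 does not show.** The two baseline-referenced analyses agree there because the within-group slope of follow-up on baseline was set to 1. In non-randomised subgroups with another slope they disagree. With equal SDs, correlation 0.5 (so slope 0.5), a 0.5 SD baseline gap and no difference given baseline, the raw gap is 0.5 × 0.5 = 0.25 SD and the change-score gap is 0.25 − 0.5 = −0.25 SD. Replacing the endpoint by a ratio to baseline could then create a mirror-image artefact.

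**5. Precision.** Adjustment leaves 1 − r² of the residual variance: 0.84, 0.75 and 0.64 for assumed r of 0.4, 0.5 and 0.6, a reduction of 16% to 36%.

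**The case against.** The best defence is that the plan is silent, not wrong. No method is given for any continuous outcome, and nothing says raw AMH will be tested between subgroups. Section 3.2 groups AMH values under ovarian function on both sides of chemotherapy, and Section 4.3 applies its aim to a series that starts at enrollment. The endpoint list could therefore be read as a list of follow-up times.

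Much of this stands. A reader might infer that the plan disregards baseline AMH, or that misattribution is certain; the documents support neither. What remains is that the before/after intent does not reach Section 5. The circulating tumor DNA endpoint there is written with assessments before and after stimulation; AMH is not. The multivariate models do not fill the gap, because they are logistic and Cox models with no covariates named.

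A reader might also infer that the ovarian-reserve entry criterion, "only applicable for patients who undergo controlled ovarian stimulation for embryo/oocyte cryopreservation", makes baseline AMH differ by design among the women compared. It does not establish this. The FSH, follicle-count and AMH conditions are joined by and/or, so as written a woman with low AMH can qualify on another marker. Stimulation status is also not one of the ovarian-function subgroups.

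Two further objections stand. The reserve remaining after treatment is useful for counseling in its own right, so the absolute values should stay. And these are subgroup evaluations, without a power calculation, of the last-listed secondary objective.

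**Conclusion.** The point holds as a gap in the analysis, not in data collection. As written, the AMH endpoints can attribute pre-treatment subgroup differences to treatment, and no specified analysis guards against it. Age is the clearest case.

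The size of any bias in this trial is unknown. It requires a baseline gap between subgroups and a correlation between baseline and follow-up AMH, and the documents quantify neither. The rates of 14.5% to 98.6% illustrate assumed gaps of 0.25 to 0.5 SD and correlations of 0.3 to 0.7 with 565 women split equally; they are not estimates for this study. The primary endpoint is unaffected. The change should be made because the sample is already mandatory and the gap can be closed before analysis.

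**What to change.** Keep the AMH values at each time point as reported endpoints. Add to Section 5:

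- Subgroup comparisons of impact use a linear model of log-AMH at each time point, with log-AMH from the inclusion sample as covariate, plus age except when age is the subgroup.
- Values below the assay limit are handled by a prespecified rule, for example a censored (Tobit) model, or substitution with a sensitivity analysis. Low values are foreseeable, since Section 1 names premature ovarian failure as a possible effect of chemotherapy.
- Handling of missing inclusion samples is stated.
- Change from baseline in log-AMH is reported as supportive only, because it need not agree with the adjusted model.

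While editing, reconcile the last time point: Section 5 counts five years from the end of chemotherapy, whereas Table 1 and Section 4.3 schedule the last sample five years after diagnosis.

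The cost is a short amendment and slightly more analysis work, with no new visits or assays. One limit remains: all three cohorts are chemotherapy candidates, so without an untreated comparator even the adjusted result cannot separate treatment from ageing, and the report should say so.
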